If at the end of phase I the results are potentially consistent with a clinically significant effect, but do not yet meet statistical significance, we will continue the open label portion until we have enough subjects who have completed the study to increase the power from 80% to 95%. Again using a one-sample t-test with a 5% Type I error rate, this would require 15 additional completers above the 22 initially planned, or 26 subjects screened when allowing for the same expected screen failure and dropout rates.

Participant Randomization: Participants in phase II will be randomly assigned 2:1 to prazosin or

PTSD/TBI Glymphatic Protocol Version 3	VA Puget Sound IRB Protocol Template Version: 2/2015	Page 37 of 45
Revised 11/02/2018		. 1

placebo, stratified by gender and group (TBI only, PTSD only, or both). Permuted block randomization codes within each stratum will be generated by a MIRECC staff member uninvolved with this study using statistical software. This person will create one card per subject number specifying treatment assignment and will prepare double envelopes labeled with the subject number and containing the treatment group assignment card. These envelopes will be used for purposes of breaking the blind when necessitated by medical emergency when a computer and the Internet may not be available, and following study termination assessments (see section 5.7 below). In addition, the investigational pharmacist will have access to the randomization codes. No other study personnel will have access to the randomization codes.

Descriptive statistics of baseline characteristics will be calculated: demographic variables, vital signs, number and cause of TBI, mental health and substance use assessment scales, cognitive testing scores, total sleep time by participant report and by actigraphy, and sleep fragmentation index as measured by actigraphy.

Primary outcome measures will be CSF total-tau, p-tau181, and Aβ42. For each outcome, we will use a linear regression model to compare, between treatment groups, the within-subject changes in biomarkers from baseline. The model will include concentration at study completion as the response (dependent) variable, and the concentration at baseline and treatment group as the predictor (independent) variables, along with the covariates age, gender, APOE\*4 status, and blast exposure quantification. To account for dropouts and subjects who have their final biomarker assessment prior to 10 weeks, we will also use a linear mixed-effects regression model with biomarker concentration as the response variable, and the predictor variables time, treatment group, and a time by treatment group interaction term, along with the same covariates as for the linear regression model. Exploratory analyses will be conducted of the interaction among biomarkers; sleep and ambulatory monitoring variables; participant-reported symptoms of PTSD, depression, and postconcussive symptoms; and cognition.

Data will be analyzed by co-investigator [name], with consultation as necessary with the MIRECC biostatistician, [name], regarding the analysis plan and interpretation.

Data Management: All study information will be recorded on standardized CRFs. Forms will be labeled with study code numbers only. Code numbers will be assigned sequentially, and will not include participant initials or any other personally identifiable information. Source documents, which may include identifying information, will be maintained in locked files within a locked office. The study coordinators at VA Puget Sound and Madigan will keep the key between the identity of participants and study code number. The key will not be shared with to anyone other than members of the research team.

The VISN-20 Northwest Network MIRECC ([name], Director; [name]) will supervise database design, double data entry, and any required computer programming. The MIRECC will provide maintenance of computer hardware and software at VA Puget Sound. Initial and second data entry will be performed on a weekly basis at VA Puget Sound by the study Research Assistant under the supervision of the MIRECC Database Manager. The Database Manager will generate weekly reports of data discrepancies. The study Research Assistant under the supervision of the Study Coordinator and Data Manager will be responsible for rectifying data entry errors on a weekly basis. Database maintenance includes nightly backup of hard drives and storage of backups at a safe off-site location. Only personnel having the

PTSD/TBI Glymphatic Protocol	Version	3
Revised 11/02/2018		

correct user name, password, and signing on from a computer with the appropriate IP address will have access.

**Disposition of Data:** CRFs will be kept at VA Puget Sound. Data will be retained for six years after study closure, at which point it will be destroyed per guidelines in place at the time of destruction. Exceptions are if a participant agrees to specimen/data banking, data will be retained indefinitely. The link between study code and participant identity will be retained for the duration of data retention.

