Occurrence of lightheadedness, dizziness on standing, palpitations, drowsiness, headache, nausea, nasal congestion, peripheral edema, and other adverse effects will be rated by a clinician as absent, present, ongoing, worsening or unacceptable. The clinician will also assess if these side effects are due to factors that may be unrelated to the medication (i.e., if the participant has been ill or is dehydrated) For vital signs parameters, unacceptable side effects will include supine hypotension (supine systolic BP<100) and clinically meaningful orthostatic hypotension ( $\geq 20$ 

PTSD/TBI Glymphatic Protocol Version 3	VA Puget Sound IRB Protocol Template Version: 2/2015	Page 27 of 45
Revised 11/02/2018	M	

mmHg drop in systolic BP accompanied by dizziness, lightheadedness or syncope).

For participants maintained on other antihypertensive medications, their primary care provider will be informed of clinically significant blood pressure reductions at any time during the study to allow adjustment of the participant's antihypertensive regimen. As a further precaution, male participants will be advised to sit on the toilet for urination during the first night of medication use. Participants will be asked to call a study clinician the day after the first dose to make sure there was no occurrence of postural dizziness.

If a participant has unacceptable side effects, the dose will be reduced to the previous titration step. Participants who cannot tolerate the dose of 1 mg morning, 1 mg afternoon and 4 mg bedtime will be reduced to the dose of 1 mg morning, 1 mg afternoon and 2 mg bedtime. If the participant is unable to tolerate a minimum dose of 1 mg morning, 1 mg afternoon, and 2 mg bedtime, he/she will be terminated from the study.

If a participant is unable to make it to a titration visit (due to illness, scheduling, etc.), the participant will be offered the option of completing the visit via the telephone; this visit will include all of the elements of a regular titration visit except for those that must be done in person, such as vital sign assessment. Alternatively, if the participant is not able to complete the study visit at all, the study clock will be "stopped" temporarily and his/her dose will be maintained at the current level until he/she is able to come for another titration visit. The titration period can be extended up to an additional three weeks in that manner.

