Study Treatment Period: Once the participant has reached his/her highest tolerated dose, he/she will enter the Study Treatment Period. The participant will maintain this dose for a minimum of 5 weeks. A clinic visit will take place at one and four weeks after stable dose is achieved to assess for adverse events. Concomitant medications and health status will be updated. Study drug adherence will be tracked by pill counts.

At the 4 week stable dose visit, we will place the ambulatory blood pressure monitoring equipment, and the participant will be sent home with the Actiwatch and sleep diaries and told to wear them as before.

After 5 weeks at stable dose, participants will undergo cognitive/behavioral testing and sample collection visits just as in baseline visits 1 and 2 (with the exception that blood will not be collected). Ambulatory heart rate measurements will be collected during and following the end of study 1 visit, again as during the baseline period.

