However, ambulatory monitoring will not be done any more than two weeks past baseline LP nor once prazosin has been started, and end of study measures will not be completed any more than two weeks past baseline LP nor once prazosin has been stopped. If necessary, an additional period of up to two weeks delay after the baseline LP but prior to the initiation of prazosin may be added to accommodate this or other scheduling difficulties in obtaining baseline ambulatory monitoring data, and an additional period of up to two weeks of taking the achieved stable prazosin dose may be added to the end of the study in order to accommodate this or other scheduling difficulties in obtaining end of study ambulatory monitoring data. Overnight blood pressure monitoring will not be performed within the 7 day period immediately prior to an LP, to ensure that this procedure does not change the results of the laboratory results via an impact on sleep.

Although all efforts will be made to complete study visits in person, it may be necessary to obtain assessments by telephone. The following actions will be attempted (as appropriate per visit schedule): 1) adverse events will be assessed, 2) assessments shall be completed by telephone interview with the raters, 3) self-rated measures will be provided to participants, then returned by mail using prepaid envelopes, and 4) dispensing of study drug shall be done by trackable shipment. No-show, missed visits and actions taken will be documented in the study record.

In general, we expect that ambulatory monitoring equipment will be returned by participants in person at subsequent visits. If, however, a schedule change, early termination or other unplanned alteration (e.g., a participant forgets to bring it to a visit as planned), there will be two alternative methods for collecting the equipment: first, a member of the study team may go to the participant's location in the community to receive the item from them, or, second, the item can be mailed back using postage-paid, self-addressed packing.

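### The supporting mixed model in section 5.5 enters its covariates without time interactions, so they do not adjust the treatment effect, and it leaves the coding of time unstated

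*Combined protocol and SAP*

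**What the plan says.** Section 5.5 (Data Analysis) gives two models for each of CSF total tau, p-tau181 and Aβ42.

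- **Regression.** "The model will include concentration at study completion as the response (dependent) variable, and the concentration at baseline and treatment group as the predictor", with age, gender, APOE*4 status and blast exposure as covariates. It has no time term.
- **Mixed model.** It is introduced by "To account for dropouts and subjects who have their final biomarker assessment prior to 10 weeks". It is specified "with biomarker concentration as the response variable, and the predictor variables time, treatment group, and a time by treatment group interaction term". The regression's four covariates are carried over. Time by treatment is the only interaction listed. The coding of time, the random effects, the contrast to be reported and the week at which it is read are not given.

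CSF is collected at baseline and at the end of treatment only. Section 5.4 lets the week of the final LP vary:

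- "Once the participant has reached his/her highest tolerated dose, he/she will enter the Study Treatment Period"
- "The titration period can be extended up to an additional three weeks in that manner"
- Under the exceptions to the visit schedule, "an additional period of up to two weeks of taking the achieved stable prazosin dose may be added to the end of the study". The same paragraph lets the first dose lag the baseline LP by up to two weeks.

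Section 5.6 asks participants who choose to withdraw early to attend the final visits, so some end LPs may come early.

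**The concern.** There are two separate points about the mixed model.

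**Covariates.** A reader told that the model carries the regression's covariates will expect an adjusted treatment effect. With two visits per person, a covariate without a time interaction shifts both visits equally and so says nothing about change. The two models would then differ in adjustment as well as in their handling of missing data, and any difference between their results would be hard to read.

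**Time scale.** The stated reason for the model, final LPs before week 10, suggests that time means elapsed weeks. The treatment effect is then a slope per week, and is forced to be proportional to weeks since baseline. Aim 1 concerns the effect of a titration period plus five weeks at steady dose. The number of weeks this takes depends on tolerability and scheduling, and two LPs per person cannot show whether the effect is linear in time.

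**Working it through.** **Inputs from section 5.5.** Baseline mean 294 and SD 54 ng/L; within-person correlation 0.98; target effect about 5%; 40 prazosin and 20 placebo completers.

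- SD of change = 54 × √(2 × (1 − 0.98)) = 10.8 ng/L, which reproduces the plan's figure.
- Target effect = 0.05 × 294 = 14.7 ng/L.
- SE of the difference in mean change = 10.8 × √(1/40 + 1/20) = 2.96 ng/L.

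The plan states no figure for the mixed model.

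**1. Covariates**

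Let d = end value − baseline value for one person. A main-effect covariate adds the same amount to both values and drops out of d. With complete pairs at a common time, the time-by-treatment estimate is the difference in mean d between arms, with or without the covariate.

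| Data (simulated, 40:20) | Largest change in the estimate on adding main-effect covariates |
|---|---|
| Complete pairs, common end time | Zero to rounding (about 1e-13 or smaller) |
| Complete pairs, unequal end times, time in weeks | 0.15 ng/L |
| 30% with a baseline value only | 0.45 ng/L |

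A REML fit to one data set gave −16.687 both ways.

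The gain from covariate-by-visit terms depends on how far the covariates predict change, which the documents do not give:

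- *Assumed 8 ng/L per covariate SD:* the SD of the estimate falls from 3.61 to 2.98. Arithmetic agrees: √(10.8² + 8²) × √(1/40 + 1/20) = 13.44 × 0.274 = 3.68 unadjusted, against 2.96 when the covariate is accounted for.
- *No covariate effect on change:* the SD goes from 2.78 to 2.82, so the extra terms cost almost nothing.

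The mean estimate did not move materially in either case.

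**2. Time scale, if time is elapsed weeks**

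With one baseline and one end value per person and correlation 0.98, the slope in an arm is close to Σ(T·d)/Σ(T²), where T is the week of the final LP. If the true effect is a constant D at every end LP, the effect read at week 10 is D × 10 × E[T]/E[T²]. Take D = −14.7. The timing shares are assumptions; the remaining participants are at week 10.

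| Final-LP timing | E[T] | E[T²] | Factor | Week-10 effect (ng/L) |
|---|---|---|---|---|
| All at week 10 | 10 | 100 | 1.000 | −14.7 |
| 10% at week 4 | 9.4 | 91.6 | 1.026 | −15.1 |
| 30% at week 4 | 8.2 | 74.8 | 1.096 | −16.1 |
| 30% at week 6 | 8.8 | 80.8 | 1.089 | −16.0 |
| 30% at week 13 | 10.9 | 120.7 | 0.903 | −13.3 |
| 30% at week 15 | 11.5 | 137.5 | 0.836 | −12.3 |
| 15% at week 4, 15% at week 13 | 9.55 | 97.75 | 0.977 | −14.4 |

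Week 15 uses every on-drug extension: 5 + 3 weeks of titration, 5 stable, 2 added. A constant effect at week 4, still within the titration schedule, is a strong assumption, so the early rows are outer cases.

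In simulation (300 runs per case), visit coding gave −14.6 to −14.8 whenever the truth was a plateau. With no true effect and 30% finishing early, rejection was 4.3% with continuous time and 3.3% with visit coding, so there was no sign of type I inflation. When the truth was proportional to weeks and 30% finished early, the slope gave −14.5 at week 10 and visit coding gave −12.6.

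**The case against.** The strongest reply is that these points touch only a supporting analysis. The baseline-adjusted regression comes first in section 5.5, adjusts for all four covariates and has no time term; the mixed model is introduced as an addition. That is the natural reading, and it limits what is at stake. It does not remove the need to say which model decides.

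Second, the text says only time. A two-level visit factor also fits the words, and the proportionality problem then disappears. This stands, so the second point is conditional.

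Third, the documents give no time course, and a plateau is an assumption. If the effect grows with weeks on drug, visit coding misses the week-10 effect by about 2 ng/L (−12.6 against −14.7), much the same size as the errors in the table. This stands too, and is why actual weeks belong in a sensitivity analysis. The largest table error, 2.4 ng/L, is also below one standard error (2.96).

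A reader might infer that week-7 and week-15 finishers have the same steady exposure but are modelled as if one had twice the effect. The documents do not support that. Stopping titration early means a lower dose, and a week-15 finisher may have seven stable weeks rather than five. Titration weeks are also weeks on drug.

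A reader might also object to the free baseline difference between arms. Under randomisation both models then target the same mean difference when end times are common, and at a correlation of 0.98 the variance ratio is (1 + 0.98)/2 = 0.99, a loss of about 1%.

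**Conclusion.** The covariate point holds as the plan is written. In the mixed model the stated adjustment does not reach the treatment effect: exactly so in complete pairs at a common time, nearly so otherwise. The consequence is lost precision and a mismatch with the regression. Reading it as bias goes too far, because under randomisation the unadjusted contrast is still unbiased. The size of the loss depends on an assumed covariate effect on change and could be nil.

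The time-scale point holds only conditionally. Error requires elapsed-week coding, unequal final-LP weeks and a non-linear effect, all together. Under the assumed mixes it runs from about 10% too large to 16% too small, with opposite errors partly cancelling when early and late LPs mix. A general claim that the mixed model misstates the drug effect is not supported, nor is one that its test is invalid.

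Neither point affects the baseline-adjusted regression. This is an inexpensive clarification and improvement to a supporting analysis.

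**What to change.** In section 5.5:

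1. Name the baseline-adjusted regression as the primary analysis for each biomarker and the mixed model as supporting.
2. In the mixed model, code visit as baseline or end of treatment, with a common baseline mean for the two arms. State the random effects, and report the treatment difference at the end visit.
3. Enter age, gender, APOE*4 status and blast exposure each with its visit interaction.
4. Use actual weeks from first dose to final LP only in a sensitivity analysis.

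The cost is wording and a few more model terms; no visit, sample or sample size changes. One trade-off should be stated in the plan: if the effect grows with time on drug, the visit-coded estimate is the average effect at the times actually measured, not the week-10 effect. The sensitivity analysis in item 4 would show this.

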### 5.6 Withdrawal of Subjects

There are three conditions under which participants will be withdrawn from the research independent of participant request:

- 1. If the participant is not able to tolerate a minimum dose of 1 mg morning, 1 mg afternoon, and 2 mg bedtime of prazosin, he or she will undergo early termination. Such participants will be referred back to their primary or referring providers for further management; if they do not have such providers, Veterans will be offered a referral to an appropriate VA provider, and non-Veterans and requesting Veterans will be provided with appropriate community referrals. Reasons for early discontinuation or withdrawal will be recorded.
- 2. Participants may be discontinued prematurely from study treatment to manage deterioration of clinical status. Any participant who: (1) reports active suicidal ideation with intent and/or with plan, (2) displays a marked deterioration of clinical and/or functional status, or (3) is otherwise judged by the study clinician to be not stable enough to continue participation, including due to any other indication of severe participant distress or presentation of immediate danger to self or others, will be discontinued from the study for management of acute or unstable symptoms. For participants whose status necessitates emergent care, study termination will be followed by a warm hand-off to appropriate VA Emergency Department personnel for emergent care. For participants who are discharged from the study due to acute symptoms or clinical deterioration that does not require emergent care, referral to appropriate VA personnel for Veteran participants or referral for appropriate community care for non-Veteran or requesting Veteran participants will be provided.
- 3. Participants who are unable to come to regularly scheduled visits or who are noncompliant with study procedures or taking medication will also be withdrawn from the study. Reasons for early discontinuation or withdrawal will be recorded.

Participants may remain in the study despite declining ambulatory heart rate or blood pressure monitoring, genetic testing, and/or quantification of cannabis consumption, as long as the study staff working with the participant continue to feel he or she is able to continue in good faith and it remains clinically appropriate. However, a participant cannot decline any screening procedures, the PCL, the PVT and emotional Stroop, the PSQI, the LP, or the prazosin titration and remain in the study (except in the circumstance that the participant is already participating in an allowed substituting prazosin titration as described above). In these cases, any participant will be considered withdrawn from the study.

Participants who withdraw early from the study due to their own decision will be thanked for participation. They will be asked to undergo the two final study visits (for ITT analysis purposes) but will not be required to have these visit (prazosin may be discontinued abruptly without adverse consequences). They will be asked why they decided to withdraw early so we can record

PTSD/TBI Glymphatic Protocol Version 3	VA Puget Sound IRB Protocol Template Version: 2/2015	Page 39 of 45
Revised 11/02/2018		· T

the reason. The participant will be notified that any data and/or samples collected will be continued to be used in the analyses unless the participant specifically requests that samples and data not be used. If the participant requests, samples (including DNA) will be destroyed.

Participants who withdraw from the study or are withdrawn by the PI will be reimbursed on a pro-rated basis for the visits they have completed, as long as all ambulatory monitoring equipment has been returned; if this equipment is not returned, all payments outstanding will be placed on hold until it is returned.

For participants completing the entire trial, the blind will be broken by a Study Clinician at the end of the study (except if they are participating in a simultaneous prazosin study: in those cases, the blind will be broken when the longer study period ends). Maintaining the blind until all participants have completed the protocol and the database has been locked would be ideal; however, previous studies have shown that optimal safety and follow-up patient care argues in favor of breaking the blind for each person when they complete the trial. All participants will be given the option of treatment with open-label prazosin after study completion (an important condition for recruitment, given that prazosin is clinically available). The appropriate and safe method for initiating open-label prazosin differs depending on whether the participant had been randomized to prazosin or placebo. For those randomized to prazosin and wishing to continue, subsequent open-label prazosin should be kept at the maximum achieved dose, and may be titrated further upward, if additional clinical benefit might be obtained. On the other hand, participants randomized to placebo will require titration to effect, as per the study titration schedule, initiated at a low dose (1 mg) to avoid the risk of first-dose hypotension.

Once the blind has been broken for a participant, they will be provided a written report describing the information from their ambulatory blood pressure and actigraphic monitoring data. These will be provided as a standardized report, generated by the analysis software for these systems. The participant will be informed that these are not being conducted as medical tests but rather as experimental data collection, and the data is being provided for their interest, rather than as the result of a medical test. We will be able to discuss the reports with the participants and refer them to their primary care provider if follow-up is warranted.

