#### **Description of Study Personnel:**

Study Clinicians: will perform safety assessments and examinations, make decisions regarding the dose titration schedule for individual participants, and make any necessary unscheduled dose changes. The Study Clinician will be a physician, physician assistant, or nurse practitioner with experience conducting clinical research in Veterans with TBI and with PTSD.

Study Raters: will administer all interview-based assessments. Raters will be master's level social workers or other study professionals who have extensive experience in performing these assessments in this study population.

Psychometrists(s) and/or Neuropsychologists: will administer all neuropsychological testing (as described in the study procedures section below). Psychometrists will be experienced and will have been trained by a neuropsychologist.

Study Coordinator(s) and Research Assistant(s): will be responsible for scheduling visits, conducting the portions of study visits that do not require clinicians, maintaining case report forms (CRFs), preparing reports for the IRB and subcommittees, and assisting the data manager.

Data Management: Database design, any required computer programming, and maintenance of computer hardware and software will be performed by the Data Management team. Initial and second data entry will be performed on a weekly basis by a study Research Assistant under the supervision of the Database Manager. The Database Manager will generate weekly reports of data discrepancies. The study Research Assistant under the supervision of the Study Coordinator and Data Manager will be responsible for rectifying data entry errors on a weekly basis.

Database maintenance includes nightly backup of servers and storage of backups at a safe offsite location. Only personnel having the correct user name, password, and signing on from a computer with the appropriate IP address will have access.

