#### 5.3 Inclusion/Exclusion Criteria

#### Inclusion criteria:

- Age ≥ 21 years
- Veteran of the U.S. Armed Forces
- Ability to complete psychometric and other clinical assessments in English
- No clinically significant laboratory abnormalities at screen
- Platelet count >100,000/mm2 within two weeks of lumbar puncture (LP)
- Body mass index (BMI) between 18 and 36 inclusive (BMIs outside this range may make LPs for CSF collection difficult to perform). If a potential participant has a BMI over 36 but still in the 30s, they may be included if the clinician determines an LP would not be difficult to perform.
- Women of childbearing potential must agree to abstain from sexual relations that could result in pregnancy or use an effective method of birth control acceptable to both participant and the study clinician during the study. Men are not required to use contraception during the study
- Meeting criteria for at least one of the following:
  - 1. History of mild or moderate TBI:
    - Exposure to at least one blast or experiencing at least one collision of the head associated with acute symptoms that meet VA/DoD criteria for mild or moderate TBI (loss of consciousness, if present, <24 hours; posttraumatic amnesia, if present, <1 week; Glasgow Coma Scale (if available) 9-15)

    - o >6 months since last TBI.
  - 2. Documented diagnosis of PTSD related to combat trauma (from any conflict)

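### A Study Clinician unblinds each phase II completer while blocks are still filling, so staff who titrate, rate side effects and discontinue may be able to deduce some later assignments

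*Combined protocol and SAP*

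**What the plan says.** - **Timing and person.** Section 5.6: for participants who complete, "the blind will be broken by a Study Clinician at the end of the study". The next sentences show that this is each person's own completion. The protocol grants that "Maintaining the blind until all participants have completed the protocol and the database has been locked would be ideal", but holds that safety and follow-up care "argues in favor of breaking the blind for each person when they complete the trial". For participants also in a simultaneous prazosin study, the blind is broken when the longer study ends.
- **Allocation.** Section 5.5, Participant Randomization: phase II is 2:1 prazosin to placebo, stratified by gender and a three-level diagnosis group. "Permuted block randomization codes within each stratum" come from a staff member outside the study. Apart from that person, only the investigational pharmacist has the code list. Neither the block size nor any variation in it is stated.
- **Study Clinician duties.** Section 4.0: Study Clinicians "make decisions regarding the dose titration schedule for individual participants, and make any necessary unscheduled dose changes". Section 5.4: side effects "will be rated by a clinician as absent, present, ongoing, worsening or unacceptable", and an unacceptable rating lowers the dose by a titration step. Section 5.6 lets the study clinician discontinue a participant judged not stable enough to continue.
- **Entry.** Discretion is limited. One example is the BMI exception in Section 5.3, where people above the limit "they may be included if the clinician determines an LP would not be difficult to perform".
- **What is absent.** No section separates the clinician who unblinds from clinicians handling later participants, or restricts who else on the team learns a revealed assignment.

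**The concern.** The restriction on the code list protects the list as a whole. Unblinding completers one at a time discloses it entry by entry. In a permuted block each revealed assignment changes the odds for the unrevealed ones, and once the remaining places all belong to one arm they are known with certainty.

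The people who may learn this hold the roles in which a guess about the arm could matter: whether to take the next titration step, whether a side effect is unacceptable, and whether someone should be discontinued. If such decisions differed by suspected arm, the dose reached and the dropout pattern could differ between arms for reasons other than the drug. The protocol plans for 30% dropout, so discontinuation is not a minor channel. Allocation concealment at entry could also weaken, though to a smaller extent.

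**Working it through.** The protocol gives no figure for predictability, so there is none to reproduce.

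**Inputs from the protocol.** Ratio 2:1, permuted blocks, gender by group (5.5). 90 enrolled in phase II and 30% dropout (5.0, 5.5). Titration 5-8 weeks (5.0). Stable dose at least 5 weeks (5.4).

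**Assumptions not in the protocol.** Block size 3, 6 or 9, or a mix of 3 and 6, known to the observer. 0.25 to 2 enrolments a week. 15% women, with diagnosis groups in equal thirds. Dropouts never unblinded.

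**Step 1, strata.** 2 × 3 = 6, averaging 90/6 = 15 participants each. Under the assumed mix, a male stratum gets 90 × 0.85/3 = 25.5 and a female stratum 90 × 0.15/3 = 4.5.

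**Step 2, delay to unblinding.** 5 + 5 = 10 to 8 + 5 = 13 weeks. At 0.5 enrolments a week a male stratum receives 0.5 × 0.85/3 = 0.142 a week, or one person about every 7 weeks. Some block-mates are therefore unblinded before the block fills.

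**Step 3, theoretical ceiling.** Suppose every earlier block member is already revealed. In a block with P prazosin and C placebo places, the expected number of certain places is the expected length of the final run, P/(C+1) + C/(P+1).
- Block 3 (2, 1): 2/2 + 1/3 = 1.333; /3 = 44%
- Block 6 (4, 2): 4/3 + 2/5 = 1.733; /6 = 29%
- Block 9 (6, 3): 6/4 + 3/7 = 1.929; /9 = 21%

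The delay in step 2 and the dropout rate mean the trial would not reach these values.

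**Step 4, with delay and dropout.** I simulated 600 trials of 90 participants per setting. For each participant, the chance of prazosin is (prazosin places left)/(places not yet revealed) in the block. The assignment is certain when this is 0 or 1.

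| Block | Certain at enrolment, at 0.25 / 0.5 / 1 / 2 per week | Certain before own treatment ends |
|---|---|---|
| 3 | 15.7 / 9.4 / 3.8 / 1.2% | about 27% |
| 6 | 7.1 / 4.5 / 1.9 / 0.4% | about 11% |
| 9 | 3.4 / 2.1 / 0.8 / 0.2% | about 5% |
| 3 and 6 mixed, sizes known | 10.2 / 6.2 / 2.7 / 0.8% | about 17% |

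The last column hardly changes with pace. It describes the final moment before a participant's own planned end, and counts dropouts as if they stayed until then. Titration comes earlier, so the share certain during titration lies between the two columns.

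Best-guess accuracy, 66.7% from the 2:1 ratio alone, reaches at most 69.1% at enrolment and 71.8% before own end. At 0.5 a week the odds at enrolment have moved off 2:1 for 20%, 43% and 55% of participants (blocks 3, 6, 9), mostly without changing the best guess.

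**Step 5, hand check for block 3.** Take full blocks finishing in enrolment order, with each earlier member revealed with probability 0.7.
- Place 1: 0.
- Place 2: first member placebo and revealed, 1/3 × 0.7 = 0.233.
- Place 3: both revealed, 0.7² = 0.49, or exactly one revealed and it is placebo, 2 × 0.7 × 0.3 × 1/3 = 0.14; total 0.63.
- Average: (0 + 0.233 + 0.63)/3 = 28.8%.

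This agrees with the simulated 27%, which is slightly lower because a stratum's last block is often unfilled.

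**Step 6, sensitivity.** If dropouts are unblinded too (all revealed at 10-13 weeks, 0.5 a week), certainty is 14% at enrolment and 42% before own end for block 3, and 10% and 25% for block 6. Best-guess accuracy before own end is then 77.1% and 73.4%. The protocol does not settle this: 5.5 refers to a section 5.7 for unblinding after termination assessments, and the contents list stops at 5.6.

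**Step 7, after the change.** If no code reaches enrolling, titrating or rating staff until the last participant has completed, certainty is 0% and best-guess accuracy stays at 66.7%.

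**The case against.** The strongest reply is that this is a disclosed trade-off with a care reason behind it. Section 5.6 explains that starting open-label prazosin safely depends on which arm the person was in, and Section 5.0 promises referrals and a bridging supply. Someone on the study side therefore needs the code. This stands, and a reader who infers that the protocol gives no reason for study-side knowledge would be wrong. What it leaves unexplained is why that person should be a clinician who may also be treating later participants.

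Other stronger readings also go beyond the documents:

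- **That staff know the block size.** The protocol is silent. Silence is a reporting gap, not evidence of fixed, known blocks, so deduction is a possibility only.
- **That 44%, 29% or 21% of assignments would be exposed.** Those ceilings assume that every earlier block member has already been revealed.
- **That rated scales are compromised.** Section 4.0 gives interviews to Study Raters and cognitive tests to psychometrists or neuropsychologists. Self-reports come from participants, who are not told others' assignments. Any effect is indirect.
- **That the primary result is biased.** The CSF assays are objective. Dose reached and discontinuation could carry an effect, but the documents give no size or direction for it.
- **That the unblinding clinician controls entry.** Eligibility is not among the listed Study Clinician duties, and the discretion shown is narrow.

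The titration schedule is fixed and some unacceptable-effect criteria are numerical blood pressure limits, which narrows judgement in titration. The other side-effect ratings, and the decision that someone is not stable enough to continue, remain judgements.

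**Conclusion.** The point holds for phase II participants randomised in this study. It does not apply to phase I, which is open label. Dual-enrolled participants receive study drug under another study and are unblinded on a different timetable. Phase II itself follows only a positive phase I.

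Within that scope, rolling unblinding by a Study Clinician undercuts the restriction on the code list, and nothing walls revealed assignments off from staff who titrate, rate side effects or discontinue. Under the stated assumptions the exposure is about 0.2-16% of assignments certain at enrolment and about 5-27% before own treatment ends, with best-guess accuracy rising from 66.7% to about 72%. It is largest with small fixed blocks, and at enrolment with slow accrual. It would be larger if dropouts were also unblinded, and smaller if staff cannot infer the block size. This is a modest weakness rather than a broken blind, and worth correcting because the correction is cheap.

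**What to change.** Keep unblinding at each participant's completion, so the post-study care rationale is preserved, and change three things:

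1. **Route of disclosure (5.6).** Have the investigational pharmacist, who already holds the codes, tell the participant and the post-study prescriber. Staff who screen, titrate, rate or analyse participants still on study should not be told.
2. **Record access (5.0 Confidentiality, 7.0).** The team keeps medical-record access for 30 days after participation ends. Limit how those staff use it, so that a post-study prazosin prescription does not reveal the arm.
3. **Randomisation list (5.5).** Specify randomly varying block sizes not disclosed to the study team. Non-disclosure is essential: with a 3-and-6 mix whose sizes are known, about 17% of assignments are still certain before own end.

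Section 5.5 should also say whether dropouts are unblinded, and correct its reference to section 5.7.

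The cost is protocol wording and a list setting, with no extra staff. The downside is that the hand-over and bridging supply must be arranged through the pharmacist and prescriber, and post-study prescribing may still reveal some assignments, so the 0% in step 7 is the best case.
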